9.6. Six-Minute Walk Test (6MWT)

Descriptive statistics of observed and change from baseline values at week 24 (Visit 8) and descriptive statistics of observed, change from baseline values, change from baseline of active treatment at week 48 (Visit 11) will be summarized by treatment group for the following measurements:

- Total Distance Walked
- Number of Laps
- Number of Rests

The number and percentage of subjects will be provided at scheduled visits by treatment group for the following categorical measurements:

- Supplemental Oxygen Used (Yes, No) prior to the 6MWT, upon completion of the 6MWT and 1 Minute after walk
- Limiting Factors to Walk (SOB, LOW Sp02, Heart Disease, Desaturation <80%, Other)

The treatment difference between Acthar and placebo for change from baseline in each assessment will be evaluated using a two-sample t-test for week 24 (Visit 8) only. A listing will be provided for the 6MWT data by subject and visit.

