	Corticosteroid taper (dosage)	≥ 50% reduction	< 50% reduction or ≥ 5 mg increase for less than 2 weeks	≥ 5 mg increase for more than 2 weeks

^aAbsolute change of predicted percentage.

Subject tolerating Acthar Gel (or placebo) will be categorized according the following scoring:

- Response is defined as scores of ≥ 3/6 points.
- Partial Response is defined as scores of 2/6 points or stable with a reduction in corticosteroid dose (ie, a total score of +1 due to ≥ 50% reduction in corticosteroid dose).
- Nonresponse is defined as scores of ≤ 1/6 points without significant corticosteroid taper (stable or deterioration in corticosteroid response).

2. PFT.
3. Imaging: HRCT; CXR (including Scadding Score).
4. Corticosteroid tapering.

5. Physician Global Assessment.
6. Patient reported outcomes (King's Sarcoidosis Questionnaire, Fatigue Assessment Scale, and Patient's Global Assessment).
7. Symptom Assessment (Medical Research Council Dyspnea Scale, Leicester Cough Questionnaire, and steroid toxicity questionnaire).
8. Functional testing: 6MWT (including Borg Scale)
9. Extra pulmonary response (ePOST score).
10. Biomarkers, (eg, for genetic testing; optional).
11. WPAI.

Endpoints:

The endpoints for this study are:

- STS response rate at 24 weeks (Visit 8).
- STS response rate at 48 weeks (Visit 11).
- Physician and subject independent responses to the question “Would you choose to continue current treatment?” at 24 and 48 weeks.
- Time to response as evaluated at earlier time points (Weeks 4 to 20), as determined by the investigator based on clinical judgment and the following parameters:
 - Patient reported outcomes.
 - Corticosteroid tapering.
 - Patient Global Assessment.
 - Physician Global Assessment.
 - PFT (at applicable time points).
 - Extrapulmonary response (ePOST).
 - Supportive efficacy endpoints per applicable time points:
 - Six-minute walk test.
 - Symptom relief (Leicester Cough Questionnaire, Medical Research Council Dyspnea Scale, steroid toxicity questionnaire).
 - CXR (including Scadding score).
- Percentage change in overall DLCO.
- Percentage of subjects with improvement in DLCO of $\geq 5\%$; $\geq 10\%$; and $\geq 15\%$.
- Percentage change in overall FVC.
- Percentage of subjects with improvement in FVC of $\geq 5\%$; $\geq 10\%$; and $\geq 15\%$.
- Percentage of improved/stable/deteriorate - side by side comparison of HRCT based on a 5-point Likert score: much worse; worse; unchanged; better; much better (central reader).

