7.2.12. Six Minute Walk Test (6MWT)

The 6MWT ([Attachment 12](#)) is objective evaluation of functional exercise capacity. It is a practical test that requires a 100-ft hallway but no exercise equipment or advanced training. It measures the distance walked on a flat, hard surface during the period of 6 minutes (treadmill are not recommended). The 6MWT evaluates the global and integrated responses of all the systems involved during exercise, including the pulmonary and cardiovascular systems, systemic circulation, peripheral circulation, blood, neuromuscular units, and muscle metabolism. It does not provide specific information on the function of each of the different organs and systems involved in exercise or the mechanism of exercise limitation, as is possible with maximal cardiopulmonary exercise testing. Changes in 6MWT after therapeutic interventions correlate with subjective improvement in dyspnea.

The 6MWT will be performed according to ATS guidelines with an improvement of ≥ 30 meters being considered as meaningful. Repeat testing should be performed about the same time of day to minimize intraday variability. The Borg Scale is used to compare shortness of breath and fatigue between baseline prior to the 6MWT test and upon completion of the 6MWT test ([ATS, 2002](#)).

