15.5. Efficacy Analysis

Efficacy analyses will be performed on the mITT Population. All efficacy endpoints will be summarized and analyzed. Pearson's chi-squared test will be used to evaluate the treatment difference between treatment groups for the categorical response endpoints. The continuous response endpoints will be analyzed using 2-sample t-test. The time-to-event endpoints will be analyzed using log-rank test. Kaplan-Meier curves will also be presented.

Additional exploratory analyses will be performed as appropriate. Such analyses may include logistic regression model, analysis of variance model, and/or mixed-effects model. Subgroup analyses based on demographics, baseline characteristics, study compliance, etc, will also be performed.

Missing data imputations will be performed as appropriate. In general, the last-observation-carried-forward method will be used to impute missing data. Additional missing data imputation may be performed as needed.

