ATTACHMENT 12: SIX-MINUTE WALK TEST

Visit 1, 8, 11

Borg Scale

0	Nothing at all
0.5	Very, Very Slight (just noticeable)
1	Very Slight
2	Slight
3	Moderate
4	Somewhat Severe
5	Severe (heavy)
6	
7	Very Severe
8	
9	
10	Very, Very Severe
	Maximal

At the beginning of the 6-minute walk test, show the scale to the patient and ask the patient this: "Please grade your level of shortness of breath using this scale". Then ask this: "Please grade your level of fatigue using this scale."

After the posttest recovery period, remind the patient of the breathing number that they chose before the exercise and ask the patient to grade their breathing level again. Then ask the patient to grade their level of fatigue, after reminding them their grade before the walk test.

Vital Signs	Baseline	Six minutes	1 Minute after walk
Heart Rate			
Oxygen Sat			
Lpm SA O ₂			
Borg Score (Shortness of Breath)			
Borg Score (Level of Fatigue)			

Laps		# of Rests	
------	--	------------	--

Limiting factors to test:

SOB LOW SpO₂ Heart Disease Desaturation <80%
 Other: _____

Total distance walked _____ Feet _____ Meters

Signature Page for VV-CLIN-023158 v2.0

Approval	[REDACTED]
	Clinical 18-May-2020 16:35:27 GMT+0000

Signature Page for VV-CLIN-023158 v2.0

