4.2. Randomization, Stratification, and Blinding

An interactive telephone/web response system will be used to allocate eligible subjects to each treatment group. Subjects will be randomized according to computer-generated allocation scheme to receive either Acthar Gel 1 mL (80 U) or placebo 1 mL administered twice a week in a 1:1 ratio. Both investigators and the subjects will be blinded to the treatment assignment. A block randomization will be performed.

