- Two baselines, baseline of overall study and baseline of active treatment, have been defined. Baseline of overall study is defined as the last assessment prior to the first dose of IMP at the double-blind treatment phase. Baseline of active treatment is defined as the last assessment prior to the first dose of active treatment in either the double-blind treatment phase or the open-label extension phase. All the analysis in the open-label extension phase that involves presenting change and/or percent change from baseline will present change/percent change from both baselines.
- Summary statistics will be provided for all study variables with descriptive statistics (number of subjects, mean, standard deviation (SD), median, minimum,

and maximum) for numerical (or continuous) variables. Frequency and percentages will be calculated for categorical variables.

- Unless specified otherwise for a given analysis, all statistical tests, when applicable, will be 2-sided with a significance level of 0.05.
- All data collected will be presented in listings, sorted by treatment group, subject identifier and date/time of procedure or event, if applicable.

All analyses will be conducted using SAS® Version 9.4 or higher. The Medical Dictionary for Regulatory Activities (MedDRA) version 23.0 will be used for coding adverse events (AEs), and medical and surgical histories. Prior or concomitant medication data will be coded according to the Anatomical Therapeutic Chemical (ATC) coding scheme of the World Health Organization (WHO) Drug Dictionary (Enhanced B2 dated March 2018 version, or higher) level 2 term.

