11.2. Genetic Profile

Genetic sample obtained for subjects who has signed the genetic inform consent form at study entry may be explored and presented in tables. Descriptive statistics will be provided if data is available.

All genetic data will be presented in a listing.

12. Interim Analysis

No formal interim analysis is planned.

13. Changes in the Planned Analysis

The summary of changes presented below reflects the changes in the planned analysis described in protocol:

- The protocol planned endpoint analysis for “Change from baseline in WPAI over time” will not be performed given very few subjects have taken WPAI questionnaire. WPAI data will be only presented in listings.
- The protocol planned endpoint analysis for “Time to response (TTR) as evaluated at earlier time points (Weeks 4 to 20) as determined by the investigator based on clinical judgment” will not be performed.
- The protocol planned analysis for biomarker and genetic endpoints may not be performed depending on the availability of the data.

14. References

Judson MA. Advances in the diagnosis and treatment of sarcoidosis. *F1000Prime Reports* 2014; 6: 89.

Mallinckrodt ARD, Inc. A Phase 4 Multicenter, Randomized, Double Blind, Placebo Controlled Pilot Study to Assess the Efficacy and Safety of H.P. Acthar® Gel in Subjects with Pulmonary Sarcoidosis. Original, 06 October 2017.

15.Appendices

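### The Week 24 six-minute walk comparison ignores baseline distance, a small and avoidable loss of precision; SAP 9.6 also names no Borg summary

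*SAP*

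**What the plan says.** SAP 9.6 summarises total distance, laps and rests at Weeks 24 and 48, plus oxygen use and limiting factors. The treatment difference "for change from baseline in each assessment will be evaluated using a two-sample t-test for week 24 (Visit 8) only". No covariate is named. This follows Protocol 15.5: "The continuous response endpoints will be analyzed using 2-sample t-test". The walk is done at Visits 1, 8 and 11 (Protocol Attachment 12), so each subject should have one pre-dose distance and, in the double-blind phase, one scheduled post-dose distance.

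The protocol synopsis lists "Functional testing: 6MWT (including Borg Scale)" among the efficacy assessments, and Protocol 7.2 repeats it. Protocol 7.2.12 gives its purpose: "The Borg Scale is used to compare shortness of breath and fatigue between baseline prior to the 6MWT test and upon completion". The same section treats a gain of at least 30 m as meaningful. SAP 9.6 mentions neither the Borg Scale nor 30 m. SAP Section 13 opens with "The summary of changes presented below reflects the changes in the planned analysis described in protocol" and then covers only WPAI, time to response, and the biomarker and genetic analyses.

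**The concern.** Subjects who walk far at screening tend to walk far at Week 24. A change score subtracts the whole baseline value, which over-corrects whenever the correlation is below 1. ANCOVA estimates how much to subtract and so leaves less residual noise. With 55 subjects and no formal sample size calculation (SAP 4.1), discarding precision that the collected data already offer is hard to justify. The SAP is not opposed to adjustment: its MMRM code in Appendix 15.4 carries the term BASVAR, although the text of SAP 9.3 does not list baseline among the covariates.

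The Borg gap is one of reporting. A measure that the protocol names as part of an efficacy assessment has no specified by-arm table, and the omission is not declared.

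**Working it through.** **Inputs from the documents**
- 55 subjects randomised (SAP 4.1).
- Allocation "administered twice a week in a 1:1 ratio" (SAP 4.2).
- Testing convention: "all statistical tests, when applicable, will be 2-sided with a significance level of 0.05" (SAP 4.3).
- 30 m as a meaningful gain (Protocol 7.2.12).

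**Assumptions, not in the documents**
- Arms of 27 and 28.
- The same SD of distance at baseline and Week 24.
- Correlation r between the two of 0.7, 0.8 or 0.9.
- SD of 100 m, only where a result in metres or power is shown.

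The documents give no power, SD or effect size for the walk, so there is no plan figure to reproduce.

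**Variance ratio.** In units of SD² per subject, the change score has variance 2(1 − r), and ANCOVA has residual variance 1 − r². The ratio is (1 − r²) / [2(1 − r)] = (1 + r)/2. The equivalent sample size under the t-test is 55 / ratio.

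| r | Variance ratio | 55 subjects are worth | Gain | CI width ratio |
|---|---|---|---|---|
| 0.7 | 0.85 | 64.7 | about 10 | 0.922 |
| 0.8 | 0.90 | 61.1 | about 6 | 0.949 |
| 0.9 | 0.95 | 57.9 | about 3 | 0.975 |

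**Small-sample check.** The formula treats the slope as known. A simulation with 27 and 28 subjects (4,000 runs per value of r) gave ratios of 0.87 at r = 0.7 and 0.96 at r = 0.9. The gain is therefore slightly smaller than the table shows.

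**Illustrative power for a 30 m difference, SD 100 m.** From t-test to ANCOVA: 30% to 34% (r = 0.7), 42% to 46% (r = 0.8), 70% to 72% (r = 0.9).

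**Is chance baseline imbalance a separate harm?** The SE of the baseline difference is 100 × √(1/27 + 1/28) = 27.0 m. The change-score estimate carries (1 − r) of a one-SE imbalance: 8, 5 or 3 m. But 2(1 − r) − (1 − r²) = (1 − r)², so this component is exactly the variance difference between the two methods. At r = 0.7, the t-test SE is 100 × √0.6 × 0.270 = 20.9 m and the ANCOVA SE is 100 × √0.51 × 0.270 = 19.3 m; the squares differ by about 8² m². The imbalance is the same precision loss, already inside the t-test's SE.

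**The case against.** The strongest reply is that SAP 9.6 does what the protocol specifies, with a valid test. The same unadjusted t-test is used for the other pulmonary function measures (SAP 9.3) and the questionnaires (SAP 9.5), and the gain from adjustment rests on assumed correlations. This stands. It makes the point an improvement rather than a correction, and a small one if r is high.

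Four stronger readings are tempting, and the documents do not support them:

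- **That a 30 m responder analysis was dropped.** Protocol 7.2.12 offers 30 m as an aid to interpretation. No such endpoint appears in Protocol 7.3 or SAP 3.2.1, so Section 13 had nothing to declare.
- **That chance imbalance biases the result by up to 8 m on top of the precision loss.** It is the same loss, as the working shows.
- **That the protocol's two Borg times conflict seriously.** Protocol 7.2.12 points to completion of the walk, whereas Attachment 12 instructs: "After the posttest recovery period, remind the patient of the breathing number that they chose before the exercise". The form in that attachment has columns for six minutes and for one minute after the walk, so it provides for both scores. What is missing is a statement of which one is the post-walk value.
- **That observed-only analysis is shown to lose the sickest subjects.** SAP Section 9 does default to observed values and 9.6 adds no imputation. But early terminators should have the Visit 8 procedures, which include the walk (Protocol 11.10, 11.5), and missed tests are made up at the next visit (Protocol 11). These rules only partly reduce missing walks, and the documents give no figure for what remains.

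On the Borg Scale, the reply is partly right. SAP 4.3 promises summary statistics for all study variables and 9.6 promises a listing of the walk data, so Borg may still be reported. Neither clause specifies a by-arm table of pre- and post-walk scores.

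**Conclusion.** The concern holds as a minor point. The t-test in SAP 9.6 is valid and matches the protocol, but it leaves out a baseline distance already collected. For r between 0.7 and 0.9 and equal SDs, adjustment would cut the variance by about 15% down to 5% and narrow the confidence interval by about 8% down to 3%. The variance ratio does not depend on the assumed SD or arm sizes, apart from the small cost of estimating the slope. The subject-equivalents use all 55 randomised and shrink in proportion if fewer have a Week 24 walk.

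The Borg omission from SAP 9.6 is real but slight. The walk is a supportive endpoint in an exploratory study and is not a component of the STS, so neither gap affects the main efficacy conclusion.

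**What to change.** 1. In SAP 9.6, analyse Week 24 change in total distance by ANCOVA with treatment and baseline distance, reporting the adjusted difference with its 95% CI. Keep the two-sample t-test as a sensitivity analysis. Visit 8 is the only scheduled post-dose walk in the double-blind phase, so no repeated-measures model is needed. Record the change of main method in Section 13, because it departs from the protocol's t-test, and make it before treatment codes are released.
2. Add a descriptive by-arm table of pre- and post-walk Borg breathlessness and fatigue, stating which post-walk time is used, or declare the omission in Section 13.
3. Optionally, report the proportion gaining at least 30 m as a descriptive aid, labelled as an addition.

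The cost is a few lines of SAP text, one short model and one table. No new data are needed.

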9.7. Extrapulmonary Physician Organ Severity Tool (ePOST)

The ePOST examines 17 extrapulmonary organs (Lung excluded) and assigns a score to each one (0 = not affected to 6 = very severely affected). The adjusted overall score will be derived as the sum of the ePOST score for each extrapulmonary organ divided by the number of extrapulmonary organs involved at any time by visit during the study.

The ePOST score assigned for each individual extrapulmonary organ will be summarized categorically using number of subjects and percentage with score from 0 (not affected) to 6 (very severe) for each treatment group by visits.

The adjusted overall score, changes from baseline and percent change from baseline, and changes and percent change from baseline of active treatment (open-label extension phase only) to each scheduled visit will be summarized by treatment group using descriptive statistics.

A listing will be provided for the ePOST data by subject and visit.

9.8. Corticosteroid Tapering

The number and percentage of subjects who have dose adjustment and justifications for dose change will be summarized at each scheduled visit by treatment group and study phase. Descriptive statistics will be provided for doses and doses change from baseline at each scheduled visit. All corticosteroid dose will be converted to prednisone equivalent dose. Additionally, weekly average prednisone or equivalent daily dose (mg/day) will be calculated from prior and concomitant medication data for prednisone collected prior to week 4 (Visit 3) and post week 48 (Visit 11) and corticosteroid use data collected between week 4 (Visit 3) and week 48 (Visit 11). The average weekly daily dose change and percent change from baseline, and change and percent change from baseline of active treatment to week (from week 25 to week 48 in open-label phase only) will be summarized descriptively by weeks from week 1 to week 24 in double-blind phase and from 25 to week 48 in open-label phase. The line plots of mean (+/- standard error) percent change of average weekly daily dose from baseline by weeks will be provided for double-blind treatment phase and overall study phase.

Subjects whose corticosteroid dosage increased for more than 2 weeks will be considered as failing to corticosteroid taper. Pearson's chi-square test (or Fisher's exact test if any expected count is less than 5) will be used to compare the treatment difference between treatment groups for the percentage of subjects who fail corticosteroid taper in double-blind treatment phase only.

Time to failing corticosteroid taper is defined as:

Time to failing corticosteroid taper (day) = date of failing corticosteroid taper - date of first dose + 1.

Time to failing corticosteroid taper will be summarized by descriptive statistics by treatment group for subjects who fail corticosteroid taper.

A listing will be provided for the corticosteroid use by subject and visit.

10. Safety Analysis

All safety analyses will be conducted using safety population for the double-blind treatment phase and open-label safety population for the open-label extension phase separately. No imputation will be applied for missing data on any safety results. Missing or partially missing adverse event start dates will be imputed for treatment-emergent AE (TEAE) justification, refer to Appendix [15.1.1](#) for imputation details. All safety data will be presented in listings based on the safety population in the double-blind treatment phase and in the open-label extension phase, respectively.

